11.4. Regulatory Review

The investigator/ sub-investigator shall not enroll any subjects prior to obtaining approval from all required local authorities, including competent authorities and radiation committee.

In addition, the investigator/ sub-investigator shall not enroll any subjects prior to obtaining approval for the registry from a properly constituted independent EC.

The investigator will submit the protocol, informed consent forms, other information to be provided to subjects such as survey instruments or questionnaires, and any proposed advertising / recruitment materials, to the EC for written approval.

CONFIDENTIAL INFORMATION

11.5. Conflict of Interest

All investigators/ sub-investigators will follow applicable laws and regulations as well as the conflict-of-interest policies of their site and the reviewing EC.

11.6. Confidentiality

All subject records will be kept confidential to the extent provided by applicable laws and regulations. The monitors and other authorized representatives of the sponsor may inspect all documents and records required to be maintained by the investigator, including but not limited to medical records.

Such records may also be reviewed by the site's EC and other regulatory bodies.

The investigator or designee will inform the subjects that their records will be reviewed.

11.7. Registry Discontinuation or Suspension

The entire registry may be suspended or prematurely terminated by the sponsor in the following cases:

- Serious adverse events as defined in section 9.1.2 attributable to the investigation.
- If new data become available which raises concern about the safety of the registry device, so that continuation of the registry might cause unacceptable risks to the subjects.
- If suspicion of an unacceptable risk to subjects arises during the registry, the sponsor may suspend the registry while the risk is assessed. The sponsor will terminate the registry if an unacceptable risk is confirmed.
- National regulatory authority withdrawal of registry approval.
- On recommendation by the CEC for any perceived safety concern based on clinical judgment, including, but not limited to, a higher than anticipated rate for any component of the safety endpoint, device failures resulting in AEs or unexpected SAEs.
- Administrative decision by the sponsor.

Registry participation of an individual registry site or an individual member of a registry site may be suspended or prematurely terminated by the sponsor in the following cases:

- If a principal investigator, EC or regulatory authority responsible for the registry has withdrawn approval for any reason.
- If sponsor monitoring or auditing identifies serious or repeated deviations on the part of the registry site or an individual registry investigator.
- If a site does not enroll any subjects.

Procedures for suspension or premature termination of this registry are:

- If the sponsor, EC or regulatory authority suspends or prematurely terminates the registry, all implanted subjects shall continue to be followed and treated as per standard of care at each site. The sponsor may request that subjects are contacted or complete an office visit prior to registry termination.
- The investigator of each site or authorized designee shall promptly inform the enrolled subjects.

CONFIDENTIAL INFORMATION

- If the sponsor received notice that the EC and/or regulatory authority approval has been withdrawn for any reason, the sponsor shall notify the investigator as soon as possible and preferably within 24 hours. Enrollment must immediately cease until such approval is reinstated.
- If the investigator receives notice that the EC and/or regulatory authority approval has been withdrawn for any reason, the investigator shall notify the sponsor as soon as possible and preferable within 24 hours. Enrollment must immediately cease until such approval is reinstated.
- If the sponsor suspends or prematurely discontinues the registry the sponsor shall inform the investigators, the ECs and the authority of the rationale and provide them with the relevant data supporting this decision.
- If the registry (or a registry site) is prematurely terminated a routine close out visit as described in section 6.4 will be performed.
- If the investigator terminates or suspends a trial without prior agreement of the sponsor, the investigator should inform the institution where applicable, and the investigator / institution should promptly inform the sponsor and the EC and should provide the sponsor and the EC a detailed written explanation of the termination or suspension.

The procedures of premature registry termination of an individual subject (voluntary withdrawal or withdrawal of the subject by the investigator) are detailed in section 5.2 of the registry protocol.

Procedure for resuming the registry after temporary suspension

- When the sponsor concludes an analysis of the reason(s) for the suspension, implements the necessary corrective actions, and decides to lift the temporary suspension, the sponsor shall obtain concurrence from the ECs and, where appropriate, the regulatory authority by providing the rational and relevant data supporting this decision before the registry resumes.
- When concurrence from ECs and, where appropriate, other regulatory authorities is obtained, the sponsor shall inform the investigators to resume the registry.
- If subjects have been informed of the suspension, the principal investigator or authorized designee shall inform them of the reasons for resumption.

CONFIDENTIAL INFORMATION

12. References

Appendix A: Eligibility Criteria with Justification / Rationale

Item Number	Text of Criterion	Rationale
I1	Patients treated with the [REDACTED] as a Bridging Stent in conjunction with a branched/fenestrated main body stent graft to allow endovascular aneurysm repair from 31 December 2021 until the 01 January 2017	[REDACTED]
I2	Age \geq 18 years at the time of implant	[REDACTED]
I3	Provision of informed consent by the patient or next of kin/legal representative (for deceased patients at registry entry, unless a waiver was granted), according to local regulations.	[REDACTED]
E1	Patients treated for ruptured aneurysm or who were otherwise hemodynamically unstable at the time of the procedure	[REDACTED]
E2	Patient treated for dissection acute or sub-acute, <90 days from presenting symptoms	[REDACTED]
E3	Patient treated using physician-modified endovascular grafts	[REDACTED] estrated and branched
E4	Patient intended to be treated with chimney, periscope octopus, sandwich technique per the pre treatment case plan.	[REDACTED]
E5	At the time of treatment, patient had known coagulation disorders including hypercoagulability that were not amenable to treatment	[REDACTED]
E6	Patient was pregnant at the time of treatment.	[REDACTED]
E7	Participation in another drug or device investigational drug or device study within one year of device implant, that can confound the registry endpoints.	[REDACTED]
E8	Patient had known or suspected systemic infection (including treatment for mycotic aneurysm) at the time of implant.	[REDACTED]

CONFIDENTIAL INFORMATION

Appendix B: Zones of Attachment

For reporting purposes, the location and extent of stent-graft coverage will utilize a system of numerically labeled zones according to Figure 4.

[figure not shown]

Figure 4 Zones of Attachment

CONFIDENTIAL INFORMATION

Protocol Modification Summary

List of Changes in VBX 21-04 protocol version #2

The following administrative changes have been made to the protocol:

- Minor typographical and punctuation errors have been corrected throughout the protocol.
- In addition, the following changes have been made to the protocol:

Section	Changes to Protocol	Rationale	Potential impact on performance, effectiveness, safety or other endpoints
Inclusion/Exclusion criteria	
Changed the wording of Inclusion criteria #1 to: Patients treated with the [REDACTED] as a Bridging Stent in conjunction with a branched/fenestrated stent-graft to facilitate endovascular aneurysm repair from [REDACTED]
 
Changed the wording of Exclusion criteria #4 to: Patient intended to be treated with chimney, periscope, octopus, sandwich technique per the pre treatment case plan.
	
Updated to extend screening and enrollment windows
 
Clarification of intent
	
[REDACTED]
 
This addition only provides clarification and will not affect study endpoints

Section 4.1 – description of the population	Maximum cap per site increased from 20 to 30 percent	Ward enrollment progression and meet powered simple size requirements	No impact
Section 5.5 – Pre-Screening	Added information about how phase one and	Adding details to clarify screening and	No impact

CONFIDENTIAL INFORMATION

	phase two of the screening will occur	enrollment timeframe extension	
Section 10.4.1 – Timing of the analysis	Added information on visit windows that will be considered for analysis	Providing clarification	No impact

CONFIDENTIAL INFORMATION

MD133246 Protocol Template

Revision#: 7

Doc Type: GC

Page 37 of 37

1.0 Introduction

This Statistical Analysis Plan (SAP) describes the statistical analyses planned to address the objectives of the [REDACTED] 21-04 to confirm the clinical performance and safety of the GORE® [REDACTED] [REDACTED] when used as a Bridging Stent with Branched and Fenestrated Endografts in the Treatment of Aortic Aneurysms involving the Renal-Mesenteric Arteries. This SAP summarizes the analyses that will be performed to confirm the safety and effectiveness of the GORE® [REDACTED] [REDACTED] and outlines tables, figures, and listings that are included in reports for the [REDACTED] clinical study.

2.0 Study Design Overview

2.1 Objectives

Primary Objective(s)

The primary objective is to confirm the clinical performance of the GORE® [REDACTED] [REDACTED] when used as a Bridging Stent with Branched and Fenestrated Endografts in the Treatment of Aortic Aneurysms Involving the Renal-Mesenteric Arteries.

Secondary Objective(s)

The secondary objective is to confirm safety of the GORE® [REDACTED] [REDACTED] [REDACTED] when used as a Bridging Stent with Branched and Fenestrated Endografts in the Treatment of Aortic Aneurysms involving the Renal-Mesenteric Arteries.

Health Economic Data Analysis

A Health Economic analysis will be performed using clinical registry data. The objective of the Health Economic analysis is to understand the value of the treatment(s) studied during the period of the registry.

CONFIDENTIAL INFORMATION

MD133254 Statistical Analysis Plan Template
Revision#: 4
Doc Type: GC

2.2 Design Summary

2.3 Study Endpoints

Primary Endpoint(s)

Primary Performance Outcome: Target vessel patency (patient level) at 12 months

Secondary Endpoint(s)

- Secondary performance outcomes:
- Reintervention (total and reintervention that can be attributed to branches originally treated with the [REDACTED] Stent Graft) at 12 months and annually through 5 years post-implant
- Target Vessel Technical Success
- Primary Technical Success (Total Endovascular Procedure)
- Target vessel instability at 12 months and annually through 5 years post-implant
- Target vessel patency, patient level, annually from 2-5 years post-implant (extended primary endpoint)
- Target vessel patency, vessel level analysis, annually from procedure to 5 years post-implant

CONFIDENTIAL INFORMATION

Page 5 of 15

Secondary safety outcomes

- Aneurysm-related mortality at 12 months and annually through 5 years post-implant
- MAEs at 30 days

Table 1. Protocol Definitions

Outcome	Definition per SVS reporting Standards
Technical Success Related Outcomes	
Target Vessel Technical Success	
Successful catheterization and [REDACTED] Stent Graft placement in all intended target vessels.
 
For this registry, technical success will be reported for the overall procedure and specifically for the vessels targeted for treatment with the [REDACTED] Stent Graft.

Primary Technical Success (Total Endovascular Procedure)	
A modified technical success definition, requiring the following:
 
 1. Successful side branch catheterization and placement of bridging stents with restoration and maintenance of flow in all intended target vessels 2. Patency of all aortic modular stent graft components and intended side branch components 3. Absence of type I or type III endoleaks at completion angiography that extends beyond 30 days by confirmatory imaging (CTA, magnetic resonance angiography [MRA], or duplex ultrasound)
Vessel Patency Related Outcomes	
Primary Patency (Primary Endpoint)	Uninterrupted patency with no occlusion or procedure performed to maintain patency on the [REDACTED] Stent Graft or native target vessel. Interventions intended to treat endoleak or stent disconnection do not count as loss of primary patency.
Primary Assisted Patency	Endovascular intervention performed to maintain patency in the presence of a stenosis before occlusion
Secondary Patency	Endovascular restoration of patency after occlusion of the side branch, stent, or stent graft has already occurred. Conversion to bypass or inability to treat by endovascular means defines loss of secondary patency

CONFIDENTIAL INFORMATION

Page 6 of 15

Occlusion	Objective documentation by angiography, computed tomography, or ultrasound of complete stent occlusion with or without minimal flow into a targeted vessel
Stenosis	Objective documentation by angiography, computed tomography, or ultrasound of stenosis intra-stent or into a targeted vessel
Kink	Objective documentation by angiography, computed tomography, or ultrasound of kink in the stented or native segment of a targeted vessel
Other Outcomes	
Intraprocedural complications	Any vessel perforation, dissection, or occlusion during target vessel stenting
Reintervention	
Any repeated vascular or nonvascular procedure related to the index procedure
 
Reintervention will be adjudicated as major or minor based on the following
 
Major: deployment of proximal or distal aortic or iliac extensions, removal of the device, use of thrombectomy or thrombolysis, and any major open surgical procedure.
 
Minor: endovascular procedures (percutaneous transluminal angioplasty, atherectomy, stenting) without thrombectomy or thrombolysis, interventions to treat branch vessel stenosis, interventions to treat type II endoleak or branch-related endoleaks, and minor surgical revisions (patch angioplasty) of the access vessels.
 
Each reintervention will be adjudicated as related to a [REDACTED] treated branch vessel component, related to a non-[REDACTED] treated branch vessel component, or related to main body component(s), if possible.

Target vessel instability	Death or rupture related to side branch complication (e.g., endoleak) or reintervention to treat a branch-related complication, including endoleak, disconnection, kink, stenosis, occlusion, or rupture
Aneurysm-related mortality	Any death that occurs within the first 30 days or any death that results from aneurysm rupture, aorta-related complications (eg, infection, occlusion, dissection, hematoma), or a complication of a secondary intervention

CONFIDENTIAL INFORMATION

Page 7 of 15

Major Adverse Events (MAEs)	
 • All-cause mortality • Myocardial infarction (MI): MI resulting in severe hemodynamic dysfunction necessitating resuscitation, cardiac arrest, or fatal outcome. • Respiratory failure requiring prolonged (>24 hours from anticipated) mechanical ventilation or reintubation • Any renal function deterioration according to the RIFLE classification system. • Bowel ischemia requiring surgical resection or not resolving with medical therapy • Permanent paraplegia (any grade 3 A-C spinal cord injury) in a patient who is no ambulatory. • Any major stroke defined according to National Institutes of Health Stroke Scale (NIHSS) or equivalent.
-----------------------------	--

2.4 Statistical Hypotheses

The registry is designed to statistically test the hypothesis that the Target Vessel Patency at 12 months (Primary Performance Endpoint) in both FEVAR and BEVAR populations of subjects is greater than 77%. The hypothesis will be tested separately in the two cohorts (FEVAR and BEVAR), using the subjects with imaging results available for the 12 months visit. The binomial exact test will be used with a one-sided 2.5% level of significance to test the null hypothesis.

The statistical hypothesis is specified as follows:

H0: $P \leq 77\%$

HA: $P > 77\%$

Alpha= 0.025 (one-sided)

Whereas P is the probability of maintaining Target Vessel Patency at 12 months.

The ITT population will be used to perform this test.

[REDACTED]

2.5 Sample Size Assumptions

The assumptions used for the calculation of sample size in the registry included the anticipated performance of the [REDACTED] Stent Graft for the FEVAR and BEVAR procedures, the acceptance criteria determined from the literature and the derived Performance Goal (PG).

[figure not shown]
[REDACTED]

CONFIDENTIAL INFORMATION

Page 8 of 15

2.6 Sample Size Calculations

3.0 Study Treatment Arms

3.1 Test Arm

Not Applicable for the observational registry

3.2 Control Arm(s)

Not Applicable for the observational registry

4.0 Study Data Collection

The validated Clinical Data Management System (CDMS) for this registry will be provided by Medrio. The sponsor keeps a separate Clinical Data Management Plan (CMMP) describing the procedures for verification, validation, and security of the CDMS. The CDMP will describe and document procedures regarding data management processes for this registry.

Once entered, data will be evaluated to confirm that it is complete, consistent, and logically sound. If changes to the data in the CDMS are required, all changes, reasons for changes, and persons making the changes will be captured in the CDMS's audit trail. Sponsor will perform periodic data reviews throughout the entire registry. Procedures and documentation for regular and ongoing data review are described in the Clinical Data Management Plan.

All registry data are targeted to be entered into the appropriate eCRF within 10 days of enrollment for the retrospective phase and within 10 days of collection for the prospective phase, however, data outside this window will not be considered a protocol deviation. Pre-Screening information will be recorded for all subjects and will only consist in inclusion /exclusion criteria evaluation, and enrollment information. All subsequent data entry will only occur after collection of informed consent to participate in the registry.

- Data Safety Monitoring Board (if applicable)
Not applicable due to the observation study design
- Clinical Events Committee

CONFIDENTIAL INFORMATION

Page 9 of 15

An independent Clinical Events Committee (CEC) will review endpoint related clinical events during the registry to ensure the consistency of endpoints reported by the site. The [REDACTED] 21-04 CEC will be comprised of an interdisciplinary team of three members with pertinent expertise who are not directly involved in the conduct of the registry.

CEC will be managed by [REDACTED] to ensure the independency of the members from the sponsor. Sponsor will not take part of any CEC activities and may only deliver initial training to the CEC members on the protocol and registry device.

After review, the CEC will inform [REDACTED] whether or not additional data is required to evaluate any specific event, whether or not clarifications are needed.

Site may need to send anonymized source documentation to CRO related to the events that need to be adjudicated by CEC. This committee will operate under pre-specified procedures as outlined in its charter. The frequency of data review and other roles and responsibilities of the committee will be

- Site Enrollment Restrictions (if applicable)

Up to 15 sites in Europe will be required to enroll a minimum of 220 patients that have had treatment with GORE® [REDACTED]® [REDACTED] when used as a Bridging Stent with Branched and Fenestrated Endografts in the Treatment of Aortic Aneurysms Involving the Renal-Mesenteric Arteries.

Each site cannot contribute to more than 10% of the total patient for each cohort without sponsor approval, with a maximum of 20% of total enrollment for a single site.

- Core lab (if applicable)

The Core Lab will perform assessments of imaging modalities according to objective process and standard procedures completed by trained and qualified personnel.

Medical imagery will be transmitted to the Core Lab using the secure, web portal functionality of the [REDACTED] System. Imaging submitted through the portal will be stripped of personal health information and replaced with appropriate registry subject identifiers in automated, systemic fashion. Recipients will process received imaging according to their standard operating procedures or registry-specific processes. Completed assessments and measurements will be reported directly in the EDC system and this data is considered source data.

- Handling of missing data

All effort will be made to minimize the missing data, however, the data not available will be treated as missing in the study and the analysis will be conducted on the available data.

5.0 Statistical Analyses

[figure not shown]
Analysis Populations

- The registry population will consist of patients that have had treatment with GORE® [REDACTED]® [REDACTED] and that meet the registry eligibility criteria.

CONFIDENTIAL INFORMATION

Page 10 of 15

Timing of Analyses

The analysis to test the primary hypothesis will be conducted once all subjects have completed their 12 Month follow-up, data has been entered and cleaned in the EDC system. Subjects with a visit within 90 days of the annual time frames (i.e., 275 – 455 for 12 Month visit) would be considered for analysis of the annual outcomes. In case of the multiple visits within the interval, the visit closest to and preceding the annual time point would be considered for the determination of the outcomes.

[REDACTED]
The subject follow-up will continue for five years, and the final analysis will be done once all subjects have completed five-year follow-up. [REDACTED]

[REDACTED] No interim analysis for the early termination of registry is planned due to the post marketing usage of the [REDACTED] Stent Graft and retrospective nature of the enrollment. In addition, once the primary analysis has been performed and hypothesis tested, further analyses may also be performed as needed for annual reports, presentations and publications based on interim data or at any other time at the discretion of Gore.

CONFIDENTIAL INFORMATION

Page 11 of 15

Analysis Populations

Intent-to-Treat (ITT) dataset will consist of all enrolled patients meeting the inclusion / exclusion criteria and treated at least one vessel with the [REDACTED] Stent Graft. A subset of the ITT dataset will be further identified of subjects with all vessels treated with [REDACTED] and another subset with all vessels treated with [REDACTED] only. ITT dataset will be used for the analysis of the primary and secondary endpoints. Similarly, per vessel analysis will be performed with all three datasets after identifying each vessel treated by [REDACTED] and also of the vessels treated without [REDACTED]

[REDACTED]

Pooling of Data

All sites in the registry will follow a common protocol and the data will be monitored to assure compliance. The data collection and handling procedures will be the same at all registry Sites. As such, there is no concern in pooling data from different sites together for analysis.

[REDACTED]

Statistical Analysis of Primary Endpoint(s)

Analysis of the Primary Endpoint to test the hypothesis will be performed using binomial exact test using one-sided 2.5% level of significance.

All subjects with follow-up visit and imaging results available from 9 to 15 months will be included in the primary analysis. Subjects with the loss of Target Vessel Patency earlier than 15 months will also be included in such analysis and considered as failures regardless of the timing and availability of another visit between 9 to 15 months.

[REDACTED]

Statistical Analysis of Secondary Endpoint(s)

[REDACTED]

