5.11. Follow Up

All follow-up performed from the index procedure to the ICF signature will be collected retrospectively. FU data will be collected from the information already present in the medical chart.

From the date of the enrollment, all FU visits including any imaging, performed according to hospital standard of care, will be collected up to 5 years post index procedure.

In addition to in person visits, remote phone follow-up is also acceptable and clinical information obtained via phone can be collected.

For testing done at institutions different than the registry site, or in case no follow-up data are available, investigators should make any efforts to retrieve documentation from the patient or from other records/sources (e.g. hospital databases, family doctor, family members).

Subjects will continue to be followed by the site's standard of care after completion of the registry.

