5.12. Subject Withdrawal from the Registry

A subject may withdraw from the registry at any time and should notify the investigator in this event. The investigator may also withdraw the subject from the registry at any time based on his / her medical judgment. The sponsor may retain and continue to use any data collected before the withdrawal of consent, if not explicitly requested otherwise by the subject.

If such withdrawal is due to problems related to the device safety or performance, the investigator shall ask for the subject's permission to follow his / her status / condition outside the registry.

CONFIDENTIAL INFORMATION

During the prospective phase, patients may be considered withdrawn for any of the following:

- Death
- Voluntary withdrawal
- Investigator withdrawal
- Any other medical condition where evaluation of the [REDACTED] is not feasible (e.g., bypassed [REDACTED], explant of the device)

If the discontinuation is caused by the development or worsening of AEs, information on the AEs must also be recorded on the appropriate eCRF. All data generated prior to patient withdrawal will be maintained, and registry data will be used as appropriate.

If possible, an additional evaluation of the [REDACTED] (s) is recommended prior to their withdrawal from the registry.

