10.4. Data Analysis

10.4.1. Timing of Analyses

The analysis to test the primary hypothesis will be conducted once all subjects have completed their 12 Month follow-up, data has been entered and cleaned in the EDC system. Subjects with a visit within 90 days of the annual time frames will be considered for analysis of the annual outcomes. [REDACTED]

[REDACTED]. The subject follow-up will continue for five years, and the final analysis will be done once all subjects have completed five-year follow-up. Separate analysis will be performed for FEVAR and BEVAR cohorts. No interim analysis for the early termination of registry is planned due to the post marketing usage of the [REDACTED] and retrospective nature of the enrollment. In addition, once the primary analysis has been performed and hypothesis tested, further analyses may also be performed as needed for annual reports, presentations and publications based on interim data or at any other time at the discretion of Gore.

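### The primary patency test has two denominators: Protocol 10.1 and SAP 2.4 use only subjects with 12-month imaging, while SAP 5.0 also counts known losses without it, and no readable text says which governs

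*SAP*

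**What the plan says.** - **Hypothesis sections.** Protocol 10.1 and SAP 2.4 use the same words: each cohort is tested separately "using the subjects with imaging results available for the 12 months visit". Both also name the ITT population.
- **Timing text.** Protocol 10.4.1 says "Subjects with a visit within 90 days of the annual time frames will be considered for analysis of the annual outcomes". The Timing of Analyses text in SAP 5.0 repeats this ("Subjects with a visit within 90 days of the annual time frames") and gives days 275–455 for month 12. Neither makes an exception for a loss that is already known.
- **Primary analysis text.** SAP 5.0 says "All subjects with follow-up visit and imaging results available from 9 to 15 months will be included in the primary analysis". Its next sentence brings in subjects who lose patency before 15 months, "considered as failures regardless of the timing and availability of another visit between 9 to 15 months".
- **Endpoint.** SAP Table 1 defines primary patency as "Uninterrupted patency with no occlusion or procedure performed to maintain patency".
- **Missing data.** Protocol 10.4.5 rules out imputation, and SAP 4.0 analyses the available data.
- **Later imaging.** Under Protocol 5.11, "all FU visits including any imaging, performed according to hospital standard of care, will be collected up to 5 years post index procedure".

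Text is redacted directly after the SAP 5.0 rule, in Protocol 10.4.5 and in SAP 7.1 to 8.0.

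**The concern.** Three patients show the problem.

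- **Occlusion documented at month 3, no scan between 9 and 15 months.** Excluded under Protocol 10.1 and SAP 2.4; a failure under SAP 5.0.
- **Patent on a month-10 scan, loss at month 14.** Has the required imaging and reads as patent under the hypothesis sections; a failure under SAP 5.0, because the loss falls before 15 months.
- **No window scan, but a month-24 scan shows all target vessels patent with no intervening procedure.** In neither denominator in the readable text, although uninterrupted patency at month 24 implies patency at month 12.

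Counting known losses is right, because uninterrupted patency cannot be regained. The imaged-only wording discards such losses. SAP 5.0 keeps them, but its readable rule gives unimaged patients a way in only if they failed, so inclusion depends on outcome.

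This is the only formally tested endpoint. The 10% inflation in Protocol 10.4.3 covers a smaller evaluable number, not inclusion that differs between successes and failures. Patients were treated from 2017 to 2021, so 12-month outcomes already exist, and an undocumented choice between the rules would look data-driven.

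**Working it through.** **Inputs from the documents.** Null rate 77%, one-sided alpha 0.025, exact binomial test per cohort, N = 100 (FEVAR) and 120 (BEVAR), 10% allowance for missed visits.

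**Plan's own figure.** Planned patency and power are redacted, so 100 and 120 cannot be reproduced. They are consistent with 90/0.9 = 100 and 108/0.9 = 120, but that is not a derivation.

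**Step 1: one extra documented loss.** With x successes in n, p = Σ(k = x to n) C(n,k) 0.77^k 0.23^(n−k). Start at the smallest passing count and add one known loss without window imaging:

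| Cohort | Imaged only | SAP 5.0 |
|---|---|---|
| FEVAR | 78/90 = 86.7%, p = 0.0159, passes | 78/91 = 85.7%, p = 0.0275, fails |
| BEVAR | 92/108 = 85.2%, p = 0.0242, passes | 92/109 = 84.4%, p = 0.0382, fails |

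One success further from the boundary, FEVAR (79/90, p = 0.0075) needs three extra losses to flip and BEVAR (93/108, p = 0.013) needs two.

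**Step 2: how often the rules disagree.** Let P be the share with no loss before 15 months (the SAP 5.0 cut), g the share without window imaging and d the share of unimaged losses that are documented. Assume g = 10% and P = 88% or 90%. Successes are captured with probability 1−g under both rules. Failures are captured with probability 1−g under imaged-only and 1−g+gd under SAP 5.0. Pass probabilities come from exact enumeration over the realised n.

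- Expected rate under SAP 5.0 = P(1−g) / [P(1−g) + (1−P)(1−g+gd)]. With d = 1 and P = 88%: 0.792/(0.792 + 0.120) = 86.8%, a bias of −1.2 points. With P = 90%: 0.81/(0.81 + 0.10) = 89.0%, a bias of −1.0.
- Expected extra losses = N(1−P)gd. With d = 1 this runs from 100 × 0.10 × 0.10 = 1.0 to 120 × 0.12 × 0.10 = 1.4.
- Power with d = 1:

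| | True 88%: imaged only / SAP 5.0 | True 90%: imaged only / SAP 5.0 |
|---|---|---|
| FEVAR | 74% / 62.5% | 90% / 83% |
| BEVAR | 82% / 72% | 95% / 90% |

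In this model the extra subjects are all failures, so every disagreement is a pass that becomes a fail, and its frequency is the gap in power: 4.5–11% of datasets if all unimaged losses are documented, 2–5.5% if half, 1–2.7% if a quarter. At true 92% with all documented it is 1–2%.

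**Step 3: type I error at a true 77%.** Suppose failed patients are a further w less likely to have a window scan (assumed), so their imaged capture is c = (1−g)(1−w).

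- *Imaged only.* The apparent rate is 0.77/[0.77 + 0.23(1−w)]; at w = 10% this is 0.77/0.977 = 78.8%. Type I error for N = 100 / 120 is 2.2% / 2.3% at w = 2%, 2.9% / 3.1% at w = 5% and 4.4% / 5.0% at w = 10%. It passes 2.5% at w of about 3–4%.
- *SAP 5.0.* Failure capture is c + (1−c)d. With w = 0, type I error is about 0.6% at d = 1 and 1.1% at d = 0.5. With w = 10% and d = 25%, capture is 0.81 + 0.19 × 0.25 = 0.8575, the apparent rate is 0.693/(0.693 + 0.23 × 0.8575) = 77.8%, and type I error is 2.8% / 3.0%.

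Losses between 12 and 15 months after a patent window scan are a further source of disagreement and are not modelled.

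**The case against.** **SAP 5.0 is the operative rule.** The hypothesis sections are summaries, the SAP 5.0 sentence is worded as an express exception, and a programmer would probably follow it. That is fair, and it makes the repair easy. But the conflict lies within the SAP as well as between documents, the timing text carries no such exception, and no readable clause gives one passage precedence.

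**The missing route may be redacted.** This stands as a limit. A blacked-out block follows the rule directly, so the gap can be asserted only for the readable text. Hidden text could supply a route or a sensitivity analysis; it would not change what Protocol 10.1 and SAP 2.4 say.

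**SAP 5.0 is simply conservative.** A reader might infer that it always errs against the device and holds type I error below 2.5%. Step 3 shows otherwise: if few unimaged losses are documented and failures are scanned less often, it reaches about 2.8–3.0%.

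**Imaged-only is always anti-conservative.** A reader might also infer that any shortfall in scans among failures breaks the 2.5% level. It does not, because the exact test attains only about 1.9% here; the shortfall must reach about 3–4%.

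**Withdrawal after bypass or explant removes failures.** It can, in the prospective phase. But Protocol 5.12 keeps earlier data and recommends a device evaluation before withdrawal where possible, and Protocol 5.15 continues follow-up when other registry devices remain. It is a plausible contributor, not a demonstrated one.

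**The sizes rest on assumptions.** They do: missing imaging, documentation of losses and true patency are all assumed, and the Step 1 flips start at the boundary.

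**Conclusion.** The point holds and should be fixed. Two readable rules define different denominators for the only tested endpoint, and they can reverse the conclusion on the same data. Under an assumed 10% without window imaging, true patency of 88–90%, and half to all unimaged losses documented, they disagree in roughly 2–11% of datasets; with fewer losses documented or higher patency, less often.

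Both biases are conditional. If most unimaged losses are documented, SAP 5.0 understates patency by about a point at most and costs power (at true 88% with all documented, 62.5% against 74% in FEVAR and 72% against 82% in BEVAR). If failed patients are noticeably less likely to be scanned, the imaged-only rule exceeds 2.5%, and SAP 5.0 can too when few losses are documented.

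A reader might infer that the planned power is breached. The documents do not support that, because the planned patency and power are redacted.

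**What to change.** 1. State one denominator, in the same words, in Protocol 10.1, SAP 2.4 and SAP 5.0. Keep documented losses as failures without requiring a window visit, and write that exception into the timing text of Protocol 10.4.1 and SAP 5.0.
2. State one cut-off, 12 or 15 months, for which losses count, and use it throughout.
3. Unless redacted text already does so, count a patient without window imaging as a success when later imaging shows uninterrupted patency of all target vessels with no intervening patency procedure. Count a later-found occlusion of unknown onset as a failure in the primary analysis, and exclude it only in a sensitivity analysis: admitting late-proven successes while dropping undated occlusions would favour the device.
4. Report best-case and worst-case results for subjects still unevaluable.

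Keep the exact binomial test as primary. If hidden text already covers items 3 or 4, cite it from the SAP 5.0 rule.

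**Cost.** Wording in both documents and modest programming; later imaging and reinterventions are already collected. Some 12-month statuses would rest on later scans, and undated late occlusions counted as failures may lower the rate slightly. No rule recovers an occlusion that is never imaged. The change must be documented before outcome data are analysed.
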